In summary, all study participants will have a screening visit before enrollment, 4 study visits for subdermal scalp injections, and one final assessment visit at week 40. Data analysis and comparison will be measured with macroscopic photography and microscopic hair follicle photography as well as with patient surveys.

Objective:

To evaluate the clinical efficacy of platelet rich plasma (PRP) injections for non-scarring alopecia in women .

Description of Study:

Subjects receiving PRP injection will undergo the following protocol:

All subjects will be asked to wear dark, non-visible goggles during the blood draw in the beginning of the visit. 22 mL of whole blood will be drawn from a peripheral vein and then processed through a centrifuge two times thus obtaining about 3-6 mL of plasma rich in leukocytes and platelets. The doctor will leave the room for approximately 10 -15 minutes to prepare the PRP injections. The subject's scalp will be cleansed topically with alcohol and then injected with the patient's PRP using a 25-gauge needle in a 3 mL Luer-lock syringe into the subcutaneous scalp. Injections will be 1-2 cm part and the amount injected will be 0.2 mL per injection. The number of injections in the treatment group will vary from patient to patient depending on the amount of PRP that was able to be harvested from the blood draw. However,

patients can expect anywhere from 10-30 injections. There will not be more than 30 injections in any patient during any study visit.

Subjects receiving placebo (preservative-free normal saline) will undergo the following protocol: All subjects will be asked to wear dark, non-visible goggles during the blood draw period in the beginning of the visit. The patient in the control group will have a sterile needle placed by a certified doctor or medical assistant into the ante-cubital fossa of the arm but no physical blood will be taken out of the patient. The doctor will leave the room for approximately 10 -15 minutes to prepare the normal saline injections. The subject's scalp will be cleansed topically with alcohol and then injected with 0.9% normal saline, for a total of 3 mL, (0.2 mL in each injection site and 15 total injections). The injection sites will be 1-2 cm apart.

Protocol Schedule:

- 1. Study visit 1: screening visit with the clinical research team after referral from Hair loss clinic with prior baseline blood work already reviewed

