Because of the parameters of the study, a chart review and subject interview will be conducted during the screening visit. "Yes" answers to any of the following will result in inability to participate in the study.

- Previous or current use in the last 1 year of finasteride, minoxidil topical or oral, or spironolactone
- A diagnosis of non-androgenic alopecia (i.e.: another diagnosis for the alopecia)
- Abnormal Baseline ferritin, TSH, platelet count, and a negative urine pregnancy test in any pre-menopausal female in past 12 months.
- Active skin disease (Psoriasis or severe seborrheic dermatitis) of the scalp
- Active scalp infection
- Severe active blood infection
- Cuts or abrasions on the scalp
- History of surgical hair restoration
- Current or recent malignancy
- History of systemic chemotherapy or radiation
- History of thyroid dysfunction
- History of autoimmune disorder (specifically Graves disease, hashimoto thyroiditis, or systemic lupus erythematosus)
- Tendency to develop keloids
- Continued medically necessary daily use of Nonsteroidal anti-inflammatory or Vitamin E
- Platelet dysfunction syndrome
- Thrombocytopenia less than 150,000
- Diagnosis of hypofibrinogenemia
- Anticipated pregnancy or trying to become pregnant in the next 2 years
- Current or active Tobacco use

Informed Consent:

Prior to entering the study, the investigator or designated assistant will explain to each subject the nature of the study, its purpose, procedures, expected duration, alternative therapy available, and the benefits and risks involved in study participation. Subjects will be given the consent document, the opportunity to ask questions, and will be informed of their right to withdraw from the study at any time without prejudice. After this explanation and before any study-specific procedures have been performed, the subject will voluntarily sign and date and informed consent form, including photographic consent form. Prior to participation in the study, the subject will receive a copy of the signed and dated written informed consent form.

Platelet Rich Plasma (PRP) And Saline Injection Guidelines:

3-6ml of PRP will be injected into randomly assigned subjects. The same procedure will be carried out for administration of the normal saline. Both procedures are detailed above.

Safety Evaluations:

Adverse Reactions

At each visit, the subjects will be assessed for any of the following possible AEs:

- -injection site pain
- -ecchymoses

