- -systemic effects, including nausea, fatigue, malaise, flu-like symptoms, headache, runny nose, diplopia, dysarthria, generalized muscle weakness, asthenia, blurry vision, ptosis, dysphagia, dystonia, urinary incontinence, breathing difficulties, rash.

Prior And Concomitant Medications:

At the initial visit, prior and concomitant medications and therapies will be reviewed as may pertain to exclusion from the study.

Restricted Medications/Treatments:

The restricted medications and treatments prior to the study initiation are those that the investigator feels may indicate that the patient has an unstable medical condition, as described in the exclusionary criteria.

Subject Withdrawal Or Discontinuation:

Subjects may choose to withdraw from the study or may be withdrawn by the investigator at any time without prejudice to their future medical care. Any subject who does not comply with the inclusion/exclusion criteria may be withdrawn from further participation in the study.

Discontinuation Procedures:

Any subject who wishes to discontinue prematurely from the study should return to the study center for an End of Study Visit.

Adverse Event Definitions:

An adverse event (AE) is any untoward medical occurrence in a patient or clinical investigation subject which is temporally related to protocol procedures, including administration of a

pharmaceutical product at any dose, but which does not necessarily have a causal relationship with the treatment. The term AE also applies to laboratory findings or results of other diagnostic procedures that are considered to be clinically relevant (e.g., that required unscheduled diagnostic procedures or treatment measures or result in withdrawal from the study). Surgical procedures themselves are not adverse events; they are therapeutic measures for conditions that require surgery. The condition for which the surgery is required is an adverse event, if it occurs or is detected during the study period. Planned surgical measures permitted by the clinical study protocol and the condition(s) leading to these measures are not adverse events, if the condition(s) was (were) known before the start of study treatment.

Adverse events will be recorded according to CTCAE guidelines.

A serious adverse event (SAE) is any AE or adverse drug reaction that at any dose results in any of the following outcomes:

- death
- life-threatening adverse event
- inpatient hospitalization or prolongation of existing hospitalization

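### The adverse-event list assessed at each visit names only two local events, so infection, scarring, bleeding beyond bruising and arm-needle events depend on open questions, most of all after the fourth injection

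*Protocol*

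**What the plan says.** Under Safety Evaluations, Adverse Reactions, the protocol states: "At each visit, the subjects will be assessed for any of the following possible AEs". The local entries are "injection site pain" and ecchymoses. The remaining entry is a run of "systemic effects, including nausea, fatigue, malaise, flu-like symptoms, headache, runny nose", continuing with "diplopia, dysarthria, generalized muscle weakness, asthenia, blurry vision, ptosis, dysphagia, dystonia, urinary incontinence, breathing difficulties, rash".

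The Exclusion Criteria include "Active scalp infection" and "Tendency to develop keloids", as well as blood infection, broken skin on the scalp, and platelet and clotting disorders.

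Under Description of Study, PRP subjects have 22 mL of venous blood drawn and can expect 10-30 scalp injections per visit. Saline subjects have 15 scalp injections and a "sterile needle placed by a certified doctor or medical assistant into the ante-cubital fossa of the arm", with no blood taken. Both groups follow the same injection schedule, at weeks 0, 4, 8 and 24.

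Adverse events are also collected in other ways. Under Protocol Schedule, each injection visit opens with a conversation with the doctor about adverse reactions of any kind, and the surveys at weeks 0, 24 and 40 cover pain and other adverse effects. Under Adverse Event Definitions, any untoward occurrence temporally related to protocol procedures counts, with recording by CTCAE.

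**The concern.** The study procedure is local: repeated needle punctures of the scalp and one in the arm. The named list is nearly all systemic. Events that are asked for by name are generally reported more completely than events that a subject must think to raise, so a list weighted this way will tend to record headache, fatigue and runny nose more fully than a mild site infection, a small scar or a sore arm.

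The omissions also fall where the two arms are handled differently. One arm has blood drawn and receives a variable number of injections of a processed product; the other has a sham needle and a fixed number of saline injections. If the final report says that no infection or scarring was seen, a reader will want to know whether anyone looked for it by name. The protocol's Data Analysis section says only that safety parameters will be analysed, and the SAP has no safety analysis, so nothing later in the plan settles how such a statement would be supported.

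**Working it through.** No statistical calculation applies, and the plan states no figure to reproduce. The check compares the list with the procedures, the exclusion criteria and the other collection routes.

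**Step 1: count the list.** Local items: injection-site pain and ecchymoses = 2. Systemic items: 6 in the first part (nausea to runny nose) + 11 in the second part (diplopia to rash) = 17. Total 2 + 17 = 19.

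**Step 2: count the exposure**, assuming that all four injection visits are attended.
- PRP: 10 × 4 = 40 to 30 × 4 = 120 scalp injections.
- Saline: 15 × 4 = 60 scalp injections.
- Both arms: 1 × 4 = 4 arm needles.

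**Step 3: set candidate local events against the list.**

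| Event | Link elsewhere in the protocol | Named on the list? |
|---|---|---|
| Injection-site infection | Scalp infection excluded at entry | No; flu-like symptoms, malaise and rash are non-specific |
| Keloid or scar | Keloid tendency excluded at entry | No |
| Haematoma or overt bleeding | Platelet and clotting disorders excluded, reason not given | Only as ecchymoses |
| Arm needle-site event | Arm needle in both arms at four visits | Not by name; ecchymoses has no body site, so arm bruising could count |

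**Step 4: trace what is specified after each injection.** In the Protocol Schedule the doctor discussion and any survey come before that day's injection. The week 0 discussion and Survey #1 therefore precede all exposure and cannot detect a treatment-related event.

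| Injection | Next visit (gap) | Open doctor discussion | Survey | Named list |
|---|---|---|---|---|
| 1, week 0 | Week 4 (4 weeks) | Yes | None | Yes |
| 2, week 4 | Week 8 (4 weeks) | Yes | None | Yes |
| 3, week 8 | Week 24 (16 weeks) | Yes | #2 | Yes |
| 4, week 24 | Week 40 (16 weeks) | Not specified | #3 | Yes |

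Injections 1 to 3 are each followed by an open discussion with the doctor. Injection 4 is not. For that interval the sources are the 19-item list and Survey #3, which the protocol describes as qualitative information from the participant. Week 40 is also the last planned visit, and so the last planned chance to record a scar.

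**What cannot be quantified.** The documents give no event rates and no measure of how much less completely unnamed events are reported. The direction of the shortfall is a general expectation; its size is unknown.

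**The case against.** The strongest reply is that the list is not the only route. Every visit from week 0 to week 40 has some open route, by discussion or survey, and the adverse-event definition is broad enough to include all the events in question. A reader might infer from the list that infection, scarring and bleeding are never asked about. The documents do not support that: a scheduled conversation about adverse reactions at four visits, plus three surveys, is a real means of collection. This part of the objection stands, and it limits the point to completeness of capture.

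Other parts also stand:
- Bleeding is partly covered by ecchymoses.
- The exclusion criteria give no reasons. An entry such as "Diagnosis of hypofibrinogenemia" may be there because of its effect on the plasma product, so it cannot be read as a statement of bleeding risk. Arm-needle events are not screened for at all; they are a risk of the procedure.
- The systemic entry is worded as a set of examples, so the count of 17 describes the items named and is not a limit. The local entries have no such open wording.
- The same list serves both arms. A reader might infer a biased safety comparison, but none is shown, and the SAP plans no between-group safety test.

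A reader might also conclude that the neuromuscular items do not belong and should be struck out. Nothing in the available text ties them to plasma or saline, but the consent pages are not available, and whether such events are plausible here is a clinical judgement that the documents do not settle.

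What the objection does not answer is the week 40 gap. It also gives no reason why a list already in use should name so few local events for a local procedure.

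**Conclusion.** The point holds as a minor, inexpensive improvement. Of 19 named items, two are local. None names infection, keloid or scar, or arm needle-site events, and bleeding appears only as bruising. These events are recordable under the plan but are likely to be captured less completely than the named ones. The weakness is greatest in the 16 weeks after the fourth injection, where no doctor discussion is specified.

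This rests on two assumptions: that prompted events are reported more completely than unprompted ones, and that the case report form follows the protocol's list, since no form is included in the documents. If the form already carries local items or an open question at week 40, the point reduces to aligning the protocol text with it. The finding does not touch the efficacy analysis.

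**What to change.** In Safety Evaluations, Adverse Reactions:
- Add injection-site infection, keloid or scar formation, bleeding or haematoma, swelling, and arm needle-site reaction or fainting. Swelling and fainting are suggested as ordinary accompaniments of needle procedures; the documents do not mention them.
- State that the local scalp items are recorded from direct view at weeks 4, 8, 24 and 40. The scalp is already cleansed and injected at the first three of these visits and photographed at week 40.
- Extend the open discussion of adverse reactions with the doctor to week 40.
- Keep the systemic items, or ask the sponsor to confirm that they are meant for this product. Do not remove them on a reviewer's judgement.

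The cost is one list and one form page to edit and a short conversation at a visit already planned, with no added visits. The downside is a few more minor local events reported in both arms.

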The Effect of Platelet Rich Plasma on Non-scarring Alopecia

PI: [name]

NCT03689452

Document Date: 9/21-2018

The Effect of Platelet Rich Plasma on Non-scarring Alopecia: A Randomized, Controlled Clinical Trial

Identifiers: GCO: 18-1714 IF2274490

IRB: IRB-18-00297

Investigators: [name] [name] [name] [name]

Study Site:
Mount Sinai School of Medicine
Department of Dermatology

New York, NY 10028

Financial Support:

Eclipse

Protocol Version: 2

Date: 9/21/18

The Effect of Platelet Rich Plasma on Non-scarring Alopecia: A Randomized, Controlled Clinical Trial

Introduction and rationale:

The purpose of this study is to evaluate the clinical efficacy of platelet rich plasma (PRP) injections for non-scarring alopecia in women. A randomized, placebo-controlled clinical trial will be performed where patients with non-scarring alopecia will either receive injections of their own PRP or injections of normal saline (placebo). Patients in the treatment group (Group A) will have a small amount of their own blood drawn (22 mL) and have their PRP injected into their scalp. The injections will be given at weeks zero, four, eight, and twenty-four. The number of injections in the PRP group will vary slightly based on how much PRP is able to be extracted from the patients' blood. However, typical number of injections will range from 10-30 with 0.2 mL injected into each site. The placebo group (Group B) will be given the same schedule but will receive sham injections only composed of normal saline (3 mL, total of 15 injections with 0.2 mL in each injection site). In place of the blood draw, the placebo group will have a sterile needle placed into the ante-cubital fossa but no blood will be taken from the patient. Both groups will have clinical data collected at all visits, including a screening visit before enrollment and a final assessment visit at week 40, for a total of six study visits per patient. Data collection will include representative photographs of the scalp and measurements of hair thickness using a specialized camera called a folliscope as well as a standard digital camera for macroscopic photos. No hair samples will be needed for photographs and there will be no biopsies taken during this study. The results from the two groups will then be compared. Patients will also be given small surveys at the beginning, middle and end of the study to assess for any pain, adverse effects, and the level of improvement the subjects have seen.

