**The Effect of Platelet Rich Plasma on Non-scarring Alopecia**

**PI: [name]**

**NCT03689452**

**Document Date: 9/21-2018**

**The Effect of Platelet Rich Plasma on Non-scarring Alopecia:  
A Randomized, Controlled Clinical Trial**

**PI:** [name]

**Date:** 9/21/18

*Statistical analyses*

Statistical analyses will be performed using SAS version 9.4 (SAS Institute Inc., North Carolina, United States). Difference scores from baseline to week 8 and from baseline to week 24 will be calculated for both hair density and caliber. The PRP and saline groups will be compared on these difference scores using independent samples t-tests. The difference scores will also be dichotomized based on whether the change over time was positive or negative. The PRP and saline groups will be compared on these dichotomized scores using chi-square tests. All given p-values will be two tailed and a p-value of less than 0.05 will be regarded as indicating statistical significance.

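### Randomised subjects may be withdrawn at the investigator's discretion with no masking of that decision, and those withdrawn before week 8 or week 24 then have no score for the comparison at that time point

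*Protocol*

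**What the plan says.** **Withdrawal.** Under Subject Withdrawal Or Discontinuation, the protocol says that subjects "may be withdrawn by the investigator at any time without prejudice to their future medical care", with no list of reasons. The same section continues: "Any subject who does not comply with the inclusion/exclusion criteria may be withdrawn from further participation in the study". Both rules are permissive, and neither is limited to the time before randomisation or first injection. The second ends participation as a whole, not only the injections.

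**After stopping.** Under Discontinuation Procedures, a subject who wishes to leave early "should return to the study center for an End of Study Visit". The section does not list what is done at that visit, does not mention subjects withdrawn by the investigator, and does not tie the visit to an analysed time point.

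**Masking.** Under Description of Study, "All subjects will be asked to wear dark, non-visible goggles during the blood draw". No masking of the doctor, the investigator or the person assessing images is described. The PRP arm has 22 mL of blood drawn, and the saline arm has a needle placed with no blood taken. The doctor then leaves for 10–15 "minutes to prepare the PRP injections" or, in the other arm, the saline ones.

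**Analysis.** The SAP forms changes from baseline to week 8 and to week 24 for hair density and caliber. "The PRP and saline groups will be compared on these difference scores using independent samples t-tests". The same changes are then dichotomised by sign and compared by chi-square test. Neither document names an analysis population, a missing-data method, or a rule for continuing photographs after withdrawal.

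**The concern.** Randomisation protects the comparison only if the groups analysed are the groups randomised. Here a decision taken after randomisation can remove a subject from the groups compared. The person taking it has wide discretion and is not described as masked. Because the eligibility rule is optional, two subjects with the same deviation can be handled differently.

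The opportunity is greatest between weeks 8 and 24. By then the week 8 full photo evaluation has been done, the subject has spoken with the doctor at each injection visit, and the week 24 score does not yet exist. If subjects doing poorly on PRP were withdrawn more readily than similar subjects on saline, the week 24 difference would favour PRP with no true effect, and the SAP's two-sided 0.05 threshold would not deliver a 5% error rate.

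**Working it through.** **No figure to reproduce.** The documents give no sample size, power, SD, allocation ratio or expected withdrawal rate. The check has two parts: who is lost, and how much it could matter under stated assumptions.

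**Step 1. Who is lost.** A change score needs a baseline value and a follow-up value. Full photo evaluations are scheduled at weeks 0, 8, 24 and 40 (Protocol Schedule).

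| Time of withdrawal | Week 8 score | Week 24 score |
|---|---|---|
| Before the week 8 images | missing | missing |
| After week 8, before week 24 images | present | missing |
| After the week 24 images | present | present |

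The t-test and the chi-square test use the same scores, so each loses the same subjects.

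**Step 2. Size of the shift.** Assumptions: no true effect, outcome SD 1, equal arms, and a fraction q withdrawn from the PRP arm only, those lowest on a predictor that correlates ρ with the outcome. In large samples the mean of those who remain shifts by

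shift = ρ × φ(z_q) / (1 − q),

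where φ is the standard normal density and z_q its q quantile.

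- q = 0.10, ρ = 0.5: z = −1.282, φ = 0.1755, 0.1755/0.90 = 0.195, × 0.5 = 0.098 SD.
- q = 0.20, ρ = 0.5: z = −0.842, φ = 0.2800, 0.2800/0.80 = 0.350, × 0.5 = 0.175 SD.
- q = 0.10, ρ = 1 (exactly the worst responders removed): 0.195 SD.

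**Step 3. Type I error.** Simulation with 20,000 trials per setting, two-sided independent t-test at 0.05. Cells give rejection rate, with the mean shift in SD in brackets.

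| Withdrawal from PRP arm | 20 per arm | 30 per arm | 50 per arm |
|---|---|---|---|
| 10%, random | 4.8% | 5.0% | 4.8% |
| 20%, random | 4.8% | 4.8% | 5.0% |
| 10%, ρ = 0.5 | 6.0% (0.092) | 6.9% (0.095) | 7.8% (0.096) |
| 20%, ρ = 0.5 | 8.1% (0.167) | 9.8% (0.170) | 13.2% (0.171) |
| 10%, exactly the worst | 9.9% (0.183) | 12.8% (0.187) | 17.7% (0.190) |

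The shifts sit slightly below the large-sample values in Step 2, as expected in small arms.

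**Step 4. Hand check of one cell** (50 per arm, 10%, ρ = 0.5). Remaining numbers are 45 and 50. SE = √(1/45 + 1/50) = 0.205. Shift/SE = 0.096/0.205 = 0.467. Rejection ≈ Φ(−1.96 + 0.467) + Φ(−1.96 − 0.467) = 0.068 + 0.008 = 7.5%, against 7.8% simulated. The normal approximation ignores the small fall in variance from selection, so a slightly lower value is expected.

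**The case against.** The strongest reply is that this is an omission, not a stated rule: the SAP nowhere prescribes a complete-case analysis, and eligibility is a weak route to bias. Most criteria are history, diagnosis or baseline laboratory items settled at a screening visit before enrolment, and nothing shows that eligibility withdrawals would follow response. Before week 8 there is also little measured response to select on, since no full photo evaluation is listed at week 4. Withdrawal unrelated to outcome does no harm to the error rate.

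Much of this stands. The loss of subjects is inferred from how a change score is built together with the SAP's silence. The general clause, "may be withdrawn by the investigator at any time", is a more likely route than eligibility, although some criteria (scalp infection or abrasions, tobacco use, pregnancy plans, ability to keep the visit schedule) can change after randomisation. Selection on the week 8 full photo evaluation can affect only week 24.

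It does not remove the point. The withdrawal clauses are stated rules, they operate after randomisation, and nothing elsewhere in the documents offsets them.

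A reader might also infer four stronger things that the documents do not support:

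- *Every withdrawn subject leaves the analysis.* No: the first table shows that withdrawal after week 8 or week 24 images leaves the earlier scores intact.
- *The investigator knows the arm.* The text gives preparation to the doctor and withdrawal to the investigator, and does not say whether they are one person. What can be said is that no masking of the investigator is described.
- *An end-of-study image is taken and then ignored.* The early-discontinuation visit has no stated contents, so a photograph there cannot be assumed.
- *The error rate would be 10–18%.* That requires perfect selection of the worst responders in one arm only.

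**Conclusion.** The point holds as a risk that the written rules permit, not as a demonstrated bias. Discretionary, unmasked withdrawal after randomisation, followed by tests that need a week 8 or week 24 score, can produce a comparison of groups other than those randomised.

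Its size cannot be derived from the documents. Under assumed arms of 20 to 50, no true effect and withdrawal from the PRP arm only, type I error stays at about 5% if withdrawal is random. With moderate selection (correlation 0.5) it is about 6–8% with a shift of 0.09–0.10 SD at 10% withdrawn, and about 8–13% with a shift of 0.17 SD at 20%. The 10–18% from removing exactly the worst 10% is an extreme bound. Similar selection in both arms would offset at least in part. The change is worth making because it is cheap beforehand and missed images cannot be recovered later.

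**What to change.** 1. State in the SAP that all randomised subjects are analysed in their assigned arm, including those later found ineligible.
2. In the protocol, separate stopping injections from stopping follow-up. Withdrawn or ineligible subjects who still consent should be invited to the scheduled week 8, 24 and 40 photo visits. This concerns follow-up only and does not alter when injections stop.
3. Replace the change-score t-tests with a baseline-adjusted repeated-measures model that uses every available scheduled image. A subject with a week 8 but no week 24 image then still informs the week 24 estimate, if the missingness is explained by the observed data.
4. Prespecify a sensitivity analysis for data missing not at random. The model alone does not recover a subject with no post-baseline image and does not remove selection on unobserved outcomes.
5. Report withdrawals and their reasons by arm, with the number of randomised subjects lacking each score, so that the chi-square results can be read against the same denominators.

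An image from an unscheduled early-discontinuation visit should not be assigned to the nearest planned visit: the documents do not say that one is taken, and the rule is ill-defined (week 16 is equally far from weeks 8 and 24).

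The cost is protocol and SAP wording, further photo visits for withdrawn subjects, a slightly more complex model, and some dilution of the effect from subjects who stopped injections.
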